18.3 Causality and Severity Assessments

By submitting this study for review, you agree to the following statement – DO NOT ALTER OR DELETE:

The investigator will promptly review documented adverse events and abnormal test findings to determine 1) if the abnormal test finding should be classified as an adverse event; 2) if there is a reasonable possibility that the adverse event was caused by the study drug(s) or device(s); and 3) if the adverse event meets the criteria for a serious adverse event.

If the investigator's final determination of causality is "unknown and of questionable relationship to the study drug(s) or device(s)", the adverse event will be classified as associated with the use of the study drug(s) or device(s) for reporting purposes. If the investigator's final determination of causality is "unknown but not related to the study drug(s) or device(s)", this determination and the rationale for the determination will be documented in the respective subject's case history.

18.4 Reporting of Adverse Reactions and Unanticipated Problems to the FDA

18.4.1 Written IND/IDE Safety Reports

For a drug study under an IND, incorporate the following from 21 CFR 312.32 as written – DO NOT ALTER OR DELETE:

The Sponsor-Investigator will submit a written IND Safety Report (i.e., completed FDA Form 3500A) to the responsible new drug review division of the FDA for any observed or volunteered adverse event that is determined to be a serious and unexpected, suspected adverse reaction. Each IND Safety Report will be prominently labeled, "IND Safety Report", and a copy will be provided to all participating investigators (if applicable) and sub-investigators.

Written IND Safety Reports will be submitted to the FDA as soon as possible and, in no event, later than 15 calendar days following the Sponsor-Investigator's receipt of the respective adverse event information and determination that it meets the respective criteria for reporting.

For each written IND Safety Report, the Sponsor-Investigator will identify all previously submitted IND Safety Reports that addressed a similar suspected adverse reaction experience and will provide an analysis of the significance of newly reported, suspected adverse reaction in light of the previous, similar report(s) or any other relevant information.

Relevant follow-up information to an IND Safety Report will be submitted to the applicable review division of the FDA as soon as the information is available and will be identified as such (i.e., "Follow-up IND Safety Report").

If the results of the Sponsor-Investigator's follow-up investigation show that an adverse event that was initially determined to not require a written IND Safety Report does, in fact, meet the requirements for reporting; the Sponsor-Investigator will submit a written IND Safety Report as soon as possible, but in no event later than 15 calendar days, after the determination was made.

For a device study under an IDE, incorporate the following from 21 CFR 812.150 as written – DO NOT ALTER OR DELETE:

The Sponsor-Investigator will submit a completed FDA Form 3500A to the FDA's Center for Devices and Radiological Health for any observed or volunteered adverse effect that is

determined to be an unanticipated adverse device effect. A copy of this completed form will be provided to all participating sub-investigators.

The completed FDA Form 3500A will be submitted to the FDA as soon as possible and, in no event, later than 10 working days after the Sponsor-Investigator first receives notice of the adverse effect.

If the results of the Sponsor-Investigator's follow-up evaluation show that an adverse effect that was initially determined to not constitute an unanticipated adverse device effect does, in fact, meet the requirements for reporting; the Sponsor-Investigator will submit a completed FDA Form 3500A as soon as possible, but in no event later than 10 working days, after the determination was made.

For each submitted FDA Form 3500A, the Sponsor-Investigator will identify all previously submitted reports that addressed a similar adverse effect experience and will provide an analysis of the significance of newly reported adverse effect in light of the previous, similar report(s).

Subsequent to the initial submission of a completed FDA Form 3500A, the Sponsor-Investigator will submit additional information concerning the reported adverse effect as requested by the FDA.

The Sponsor-Investigator will submit a completed FDA Form 3500A to the FDA's Center for Devices and Radiological Health for any observed or volunteered adverse effect that is determined to be an unanticipated adverse device effect. A copy of this completed form will be provided to all participating sub-investigators.

The completed FDA Form 3500A will be submitted to the FDA as soon as possible and, in no event, later than 10 working days after the Sponsor-Investigator first receives notice of the adverse effect.

If the results of the Sponsor-Investigator's follow-up evaluation show that an adverse effect that was initially determined to not constitute an unanticipated adverse device effect does, in fact, meet the requirements for reporting; the Sponsor-Investigator will submit a completed FDA Form 3500A as soon as possible, but in no event later than 10 working days, after the determination was made.

For each submitted FDA Form 3500A, the Sponsor-Investigator will identify all previously submitted reports that addressed a similar adverse effect experience and will provide an analysis of the significance of newly reported adverse effect in light of the previous, similar report(s).

Subsequent to the initial submission of a completed FDA Form 3500A, the Sponsor-Investigator will submit additional information concerning the reported adverse effect as requested by the FDA.

18.4.22 Telephoned IND Safety Reports – Fatal or Life-threatening Suspected Adverse Reactions

For a drug study under an IND, incorporate the following from 21 CFR 312.32 into the response, as written:

In addition to the subsequent submission of a written IND Safety Report (i.e., completed FDA Form 3500A), the Sponsor-Investigator will notify the responsible review division of the FDA by telephone or facsimile transmission of any unexpected, fatal, or life-threatening suspected adverse reaction.

The telephone or facsimile transmission of applicable IND Safety Reports will be made as soon as possible but in no event later than 7 calendar days after the Sponsor-Investigator's receipt of the respective adverse event information and determination that it meets the respective criteria for reporting.

Not applicable.

18.5 Reporting Adverse Reactions and Unanticipated Problems to the Responsible IRB

By submitting this study for review, you agree to the following statement – DO NOT ALTER OR DELETE:

In accordance with applicable policies of The Pennsylvania State University Institutional Review Board (IRB), the investigator will report, to the IRB, any observed or reported harm (adverse event) experienced by a subject or other individual, which in the opinion of the investigator is determined to be (1) unexpected; and (2) probably related to the research procedures. Harms (adverse events) will be submitted to the IRB in accordance with the IRB policies and procedures.

18.6 Unblinding Procedures

Describe the procedures for unblinding study therapy on a subject, including documentation of this in the subject's source document. Include example(s) here why someone might unblind a study. In most cases, the unblinding will be part of managing a serious adverse reaction and will be reported with the serious adverse event. However, in cases where unblinding was not associated with a serious adverse event, such actions should be reported in a timely manner.

In rare cases, if any resident participants are determined by the research team to have a serious adverse reaction directly related to the lighting intervention, we will unblind the participants' lighting conditions.

18.7 Stopping Rules

In studies with a primary safety endpoint or studies with high risk to study subjects, provide the rules that define the circumstances and procedures for interrupting or stopping the study. If an independent Data and Safety Monitoring (DSMB) or Committee (DSMC) is set up for the study, the same stopping rules should be incorporated into the safety analysis plan as well.

Not applicable.

19.0 Study Monitoring, Auditing and Inspecting

19.1 Study Monitoring Plan

19.1.1 Quality Assurance and Quality Control

Include this section if FDA regulations apply to this study (see "WORKSHEET: Drugs (HRP-306)" and "WORKSHEET: Devices (HRP-307)". HRP-306 and HRP-307 can be accessed by clicking the Library link in CATS IRB (<http://irb.psu.edu>).

Describe how you will ensure that this study is conducted, and that the data are generated, documented (recorded) and reported in compliance with this protocol, with institutional and IRB policies, with Good Clinical Practice guidelines and any other applicable regulatory requirements.

Indicate who is responsible for monitoring the conduct of the study and specify how often the study will be monitored.

For single-site studies with low risk, it may be appropriate for the principal investigator to monitor the study.

For multi-center studies or single site studies involving significant risk, an independent monitor may be required (e.g., monitoring by the staff of the PSU quality assurance program office(s) or by a clinical research organization).

PI [name] and [name] are responsible for monitoring the conduct of the study weekly during the 13 weeks of the study. PI [name] will ensure that all surveys, lighting data, and assessments collected from the research team follows protocols and securely locked in the office through weekly review of collected data. Additionally, we will have Excel sheets to keep track of the progress of data collection to ensure all necessary data are collected.

19.1.2 Safety Monitoring

Include this section if FDA regulations apply to this study (see "WORKSHEET: Drugs (HRP-306)" and "WORKSHEET: Devices (HRP-307)". HRP-306 and HRP-307 can be accessed by clicking the Library link in CATS IRB (<http://irb.psu.edu>).

Indicate the process for identifying, recording, and reporting adverse events.

Specify roles for adverse event recording and monitoring. Indicate each staff member's role in the adverse event reporting process. Include the following if applicable:

The Principal Investigator will confirm that all adverse events (AE) are correctly entered into the AE case report forms by the coordinator; be available to answer any questions that the coordinators may have concerning AEs; and will notify the IRB, FDA, sponsor and/or DSMB of all applicable AEs as appropriate. All assessments of AEs will be made by a licensed medical professional who is an investigator on the research.

The Research Coordinator will complete the appropriate report form and logs; assist the PI to prepare reports and notify the IRB, FDA and/or DSMB of all Unanticipated Problems/SAE's.

The **Monitor** will confirm that the AEs are correctly entered into the case report forms. The Monitor will also confirm that the adverse events are consistent with the source documents and are reported to the appropriate regulatory bodies as required.

During the 13 weeks of lighting intervention, the research team will identify adverse events through interviews with CNAs using a checklist, which includes deteriorated BPSDs, skin rash, eye irritation, dizziness, nausea, or any other reactions. Data will be collected routinely once every two weeks throughout the study period or as needed by staff reporting. If there is a report of adverse events, PI [name] will ensure that these adverse events are correctly logged and entered into the AE case report forms and notify the IRB, FDA, and NIH. The research coordinator will keep track of the adverse event and assist PO [name] to prepare reports to notify IRB, FDA, and NIH.

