1.2 Primary Study Endpoints

State the primary endpoints to be measured in the study.

Research typically has a primary objective or endpoint. Additional objectives and endpoints are secondary. The endpoints (or outcomes), determined for each study subject, are the quantitative measurements required by the objectives. Measuring the selected endpoints is the goal of a trial (examples: response rate and survival).

The primary outcomes of this study are 1) the effect of SABL on residents' agitation, other BPSD, affect, sleep and any side effects, 2) fidelity of SABL (e.g., lighting level on site and at individual level), and 3) feasibility of implementing SABL (e.g., acceptability, feasibility, appropriateness, time, and cost of implementing and maintaining the lighting).

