- The test finding is accompanied by clinical symptoms. We will not be able to completely distinguish whether a clinical symptom is resulted from dementia or other comorbidities, or it is resulted from the SABL treatment. We will assess dementia-related symptoms, including behavioral and psychological symptoms at baseline and every other week throughout the 13-week study period. Also, during the 13-week study period, the SABL will only be provided for 4 weeks. When a clinical symptom occurs during those 4 weeks, we will compare the participant's symptoms with the baseline and non-intervention period to examine if the symptoms are possibly SABL-related. In addition, we will examine other comorbidities that may contribute to the clinical symptoms, such as delirium, urinary tract infection, and a new medical condition/procedure that may cause pain (e.g., tooth extraction, fall). We will collect all relevant information and document it and will observe if the same symptom occurs to other participants.
- The test finding necessitates additional diagnostic evaluation(s) or medical/surgical intervention; including significant additional concomitant drug treatment or other therapy.

NOTE: Simply repeating a test finding, in the absence of any of the other listed criteria, does not constitute an adverse event.

- The test finding leads to a change in study drug dosing or discontinuation of subject participation in the clinical research study

The test finding is considered an adverse event by the investigator.

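### Side effects are a primary outcome, but worsened behaviour is tied to SABL only by case-by-case review of SABL-period symptoms, with no SABL-versus-control comparison planned

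*Protocol*

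**What the plan says.** Protocol section 1.2 lists the effect of SABL on agitation, "other BPSD, affect, sleep and any side effects" among the primary outcomes.

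Section 19.1.2 gives the method of collection: "interviews with CNAs using a checklist, which includes deteriorated BPSDs, skin rash, eye irritation, dizziness, nausea, or any other reactions", every two weeks through all phases or as staff report. For the behavioural item it names no scale, amount, duration or reference visit.

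Section 18.2 accepts that symptoms of dementia or comorbidity cannot be fully told apart from effects of SABL. For a symptom that arises in the 4 SABL weeks, "we will compare the participant's symptoms with the baseline and non-intervention period to examine if the symptoms are possibly SABL-related". It adds that "we will examine other comorbidities that may contribute to the clinical symptoms" and that the team "will observe if the same symptom occurs to other participants". No matching step is described for symptoms that arise in the control weeks.

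Section 18.3 gives the decision to the investigator: "The investigator will promptly review documented adverse events and abnormal test findings". If causality stays unknown and the relationship is questionable, "the adverse event will be classified as associated with the use of the study drug(s) or device(s) for reporting purposes". If it is unknown but judged unrelated, the reasoning is documented instead.

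Section 9.7, on statistical tests for safety data, is marked not applicable. For Aim 1 the SAP names changes in CMAI, NPI-NH and ARS as outcomes and average light dose as the independent variable. It contains no side-effect analysis.

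**The concern.** A review that starts only from symptoms in the SABL weeks has no background rate to set them against. The criteria in section 3.1 select residents who are already agitated, so some worsening between visits is to be expected without any change of light. With no stated margin or reference visit, the number of residents called worse depends on how each interviewer and investigator reads the item, and questionable cases are resolved towards the device.

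Worsened behaviour is a harm this trial needs to be able to see. Section 2.2 cites an earlier ambient-light study in which agitation deteriorated, and section 10 lists increased agitation as a potential but rare risk. Under the present plan, a high count of SABL-related deterioration could be ordinary fluctuation, and a low count could be a strict reading of the item. Neither answers the primary question on side effects, although the crossover collects the data that could.

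**Working it through.** **Inputs from the documents**
- Visits at weeks 1, 3, 5, 7, 9, 11 and 13 (protocol 7.2).
- SABL visits are weeks 3 and 5 in the SABL-first home and weeks 9 and 11 in the SABL-second home; control visits are the reverse (7.2, Table 1).
- Usual-light visits before SABL starts: one (week 1) in the SABL-first home, four (weeks 1, 3, 5, 7) in the other.
- 40 residents, 20 per home, with 36 expected after attrition (8.1, 8.2).

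**Not in the documents:** an expected event rate, a worsening margin, or the visit-to-visit variability of any scale. There is thus no stated figure to reproduce, and every rate below is an illustration with zero SABL effect.

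**Step 1. Simplest reading: any rise over week 1 on one continuous score.** If the three scores are exchangeable, week 1 is the highest with probability 1/3. P(at least one of two SABL visits above week 1) = 1 − 1/3 = 2/3, or 40 × 2/3 ≈ 27 residents, the same in both homes.

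**Step 2. Other assumptions, still against week 1** (simulation, resident effect plus visit noise, except where a formula is shown)

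| Assumption | Share flagged |
|---|---|
| Three independent scores, any one rising: 1 − (1/3)³ | 96% |
| Two independent scores: 1 − (1/3)² | 89% |
| Baseline selected to be high (cut −0.5 to +1 SD, reliability 0.6) | 58% to 36% |
| Coarse scoring with ties (steps of 1 or 2 SD) | 52% or 38% |
| Margin of 0.5 / 1 / 1.5 / 2 within-resident SD | 52% / 37% / 23% / 13.5% |
| 1 SD margin plus baseline selected above the mean | 21.5% |

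**Step 3. Sequence.** If review is prompt, only earlier visits are available. With any rise counting and no time trend:
- Reference week 1 only: 66.7% in both homes, difference 0.
- Reference the mean of earlier usual-light visits: 66.7% for SABL-first. For SABL-second, each SABL score minus the mean of four has variance 5/4, and the two differences have covariance 1/4, so their correlation is 0.2. The rate is 1 − [1/4 + arcsin(0.2)/(2π)] = 71.8%, a difference of about 5 points.
- Worse than every earlier usual-light visit: 1 − 1/3 = 66.7% for SABL-first and 2/6 = 33.3% for SABL-second, a difference of 33 points in the opposite direction.

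**Step 4. Does a symmetric comparison remove the problem?** With the same rule against week 1 at SABL and control visits, no effect and no trend, both periods flag 2/3 and the expected difference is 0. Now add a common drift of 0.05 within-resident SD per week: weeks 3 and 5 flag 70.8%, and weeks 9 and 11 flag 78.3%. SABL minus control is 70.8 − 78.3 = −7.5 points in the SABL-first home and 78.3 − 70.8 = +7.5 in the other. The average over homes is 0.

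**Step 5. Precision of that comparison, on the Step 1 reading.** P(neither SABL visit above week 1) = 1/3, and P(none of the four visits above week 1) = 1/5. So P(flagged under control only) = 1/3 − 1/5 = 2/15, and likewise for SABL only. The discordant share is 4/15. SE = √[(4/15)/n], which is 0.086 at n = 36 and 0.082 at n = 40. The 95% half-width is 1.96 × SE, about 17 and 16 points.

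**The case against.** The strongest reply is that the protocol states no score-based trigger. The checklist is an interview with care staff, listed in Table 2 alongside the rating scales as its own item, and nothing says that any rise in a score ticks it. Attribution is also wider than a comparison with past scores: it covers the non-intervention period, comorbidities and other participants, it yields only a possible relationship, and the investigator can record an unknown cause as unrelated. All of this stands. It rules out reading the 2/3 as a prediction.

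Three stronger readings are tempting and are not supported:
- A reader might infer that most residents will be flagged. Several plausible assumptions in the working give well under half, and the documents cannot choose between them.
- A reader might infer a twofold difference between the homes. That needs a rule of exceeding every earlier visit, which appears nowhere. With a week-1 reference and no trend the difference is zero.
- A reader might infer a stream of false reports to the IRB and FDA. Section 18.5 limits IRB reports to unexpected and probably related harms, and 18.4.1 limits FDA device reports to unanticipated adverse device effects, which 18.1 defines as serious. Section 19.1.2 mentions notification without those limits, but that is a question of reconciling sections and does not show that over-reporting will occur.

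It can also be said that the SAP already models CMAI and NPI-NH, so an average worsening would appear there. That is partly true. But the model is set up for benefit, with light dose as the predictor. It does not give the proportion of residents who worsen under SABL and under control, and it does not cover the other checklist items.

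**Conclusion.** The point holds as a gap in method for a stated primary outcome. The plan's only route from worsened behaviour to SABL is an individual review of SABL-week symptoms, with an undefined threshold and an undefined reference. It plans no comparison with the control period, where the same checklist is run.

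The range of null flag rates in the working is a measure of how open the definition is, not an estimate of what will happen. It rests on scores being the trigger, on week 1 as the reference, and on assumed variability, ties, selection and number of scales. Dependence on sequence is possible but conditional: it requires prompt review, and its size and direction follow from a reference that the protocol leaves open.

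Individual causality review remains appropriate for following and reporting single events. What it cannot support is a summary statement that SABL did, or did not, worsen behaviour.

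**What to change.** Leave adverse-event capture, individual follow-up and reporting in protocol sections 18.2, 18.3 and 19.1.2 as they are. Add a side-effect analysis to the SAP:

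- Use the same checklist items at the two SABL visits and the two control visits (weeks 3 and 5 against 9 and 11, in the order of each home).
- Add one worsening criterion on CMAI and NPI-NH relative to week 1, with its margin fixed before data are seen, applied identically at those four visits.
- Count a resident as positive in a period if positive at either visit, and state how a resident with a missing visit is handled.
- Report the within-resident SABL-minus-control difference in proportions with a 95% CI. Compute it in each home and average the two with equal weight, so that a common time trend cancels.
- Base any summary statement on SABL-related deterioration on this comparison, and present the case-by-case attributions as descriptive.

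The cost is SAP wording and one small analysis of data already scheduled for collection. The limits should be stated with it. The interval will be wide at about 36 to 40 residents (roughly ±16 to 17 points in the illustration above). It reflects variation between residents in these two homes only. The contrast also assumes that nothing from the SABL period carries into the later control visits.
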